6.4 STUDY INTERVENTION COMPLIANCE

Compliance to study intervention is firstly confirmed by the patient signing the informed consent form. If patients do not want to continue treatment and finish all 4 rTMS sessions together with pre- and post-imaging and interviews, they will be excluded from the study which will be mentioned in the case report form. The data collected up to this point will not be included in the analysis because the primary outcome is the outcome measure of the HCS for which all three measures (baseline, after the last rTMS session, post-MRI) are necessary to reasonably estimate the symptom trajectory.

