8 STUDY ASSESSMENTS AND PROCEDURES

8.1 EFFICACY ASSESSMENTS

Rating

All assessments will be performed by trained raters.

Time frame

Screening procedures / evaluation must be done on the same day or the day before inclusion of the patient into the study. The reason for this is that we assess rTMS effect independently of potentially influencing antipsychotic medication effects. Therefore, patients cannot start with antipsychotic medication treatment parallel to the rTMS treatment. Clinical interviews will be conducted by trained staff.

Imaging

MRI acquisition will consist of the following: On the day of imaging, the patient will be transported to the North Shore University Hospital 3T Siemens Prisma MRI suite. The patient will undergo an approximately 55 minutes long acquisition session. All subjects will receive structural (e.g., T1) and functional (e.g. resting BOLD fMRI, DTI, and ASL) MRI exams. During the anatomical images, the participating subject will be asked not to move, during resting state fMRI, the subject will be asked to open their eyes and to think of nothing in particular, but to stay awake. The total scanning time will be approximately 55 minutes.

Assessment of instruments

The primary outcome measure is the improvement of AVH measured with the HCS.

The secondary outcome measures are:

- Qualitative outcome of the BAVQ-R
- AVH as part of positive symptoms measured with the respective BPRS-subscale
- Global functioning assessed using the CGI and GAF
- Cognitive functioning assessed using the rBANS

Structural and functional neurophysiological characteristics are investigated as predictors for rTMS treatment response.

Outcome criteria

Responder criteria:

- a. Clinically significant improvement is defined as a score of <8 on the HCS (Hoffman et al., 2013)
- b. Drop-outs: defined as patients who discontinue treatment before completing the 4 rTMS sessions.

Premature exits:

- a. Consent for study participation is withdrawn before 4 rTMS treatments have been administered, or
- b. rTMS is discontinued for clinical or other reasons before 4 rTMS have been administered, or
- c. Patient misses more than two treatments in total.

Both drop-outs and premature exits in this study will be analyzed as last observation carried forward.

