9.3 POPULATIONS FOR ANALYSES

Data of all patients who attended pre-MRI and interview, 4 sessions of rTMS, and post-MRI and interview will be included in the analysis.

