9.4 STATISTICAL ANALYSES

9.4.1 GENERAL APPROACH

Descriptive statistics will include all patients who completed the study. Patient groups (stratified according to either their sham or real rTMS treatment) will be compared concerning age, sex, socio economic status, general psychopathology (CGI, GAF), severity of AVH (BPRS-subscale, BAVQ-R), and cognitive outcome (rBANS). In particular, mean (standard deviation) together with the range (min, max) will be assessed for the two groups.

Inferential statistics: the p-value will be set to 5% and therefore every value below this threshold is considered significant. Effect sizes will be calculated as well to evaluate if we are dealing with a clinically important effect. Covariates will be included in the analyses such as age and sex.

General assumptions of heterogeneity and normality will be assessed before any subsequent analysis. Based on this either parametric or non-parametric tests will be chosen.

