9.4.2 ANALYSIS OF THE PRIMARY EFFICACY ENDPOINT(S)

Our primary goal is to examine if real rTMS for the treatment of AVH is superior to sham rTMS. Therefore, we test if symptoms decreased in patients who received 4 sessions of low-frequency rTMS for one day.

For this purpose, repeated measures ANCOVAs will be implemented with time of measurements as the within-subject factor, group (treatment vs. placebo) as between subject's factor, and baseline HCS scores as covariate.

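### Patients who stop rTMS early are excluded in 6.4 and 9.3 but carried forward in 8.1, so the primary analysis set is not defined, and either rule can bias the comparison

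*Combined protocol and SAP*

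**What the plan says.** The combined protocol and SAP gives two rules for the same patients.

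- **Exclusion.** Section 6.4, on patients who do not finish all sessions, scans and interviews: "The data collected up to this point will not be included in the analysis". Its reason is that the primary HCS outcome needs all three ratings. Section 9.3, the only population definition: "Data of all patients who attended pre-MRI and interview, 4 sessions of rTMS, and post-MRI and interview will be included in the analysis". Section 9.4.3 excludes drop-outs from the secondary analyses, and 9.4.1 adds: "Descriptive statistics will include all patients who completed the study".
- **Carrying forward.** Section 8.1 describes drop-outs as "defined as patients who discontinue treatment before completing the 4 rTMS sessions", adds three kinds of premature exit, and states: "Both drop-outs and premature exits in this study will be analyzed as last observation carried forward".

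Section 9.4.2, the primary analysis, has no missing-data rule. Its nearest hint is "we test if symptoms decreased in patients who received 4 sessions of low-frequency rTMS for one day".

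Three other places bear on this. Section 7.1 says that stopping rTMS is not leaving the study and that the remaining procedures should go ahead, whereas 1.1, 6.1.2 and 6.4 withdraw or exclude such patients. The list in 7.1 of data to collect at discontinuation does not name the HCS. Section 7.2 has treated patients who later leave replaced.

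**The concern.** A patient cannot be both left out and carried forward. While both rules stand, the analysed patients and their number depend on which section is followed, and the choice could be made after results are seen. This concerns the primary endpoint of a 40-patient trial that 9.2 offers as a possible basis for a larger study, so a few patients matter.

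Neither rule is safe by default. Some exit grounds in 7.2 can relate to outcome (worsening, antipsychotics given, side effects the patient will not endure); others, such as pregnancy or moving, need not. Dropping leavers biases the comparison if outcome-related exit differs between arms in rate or in reason. Carrying forward has its own difficulty: section 3 fixes the baseline HCS at 10 for everyone, and 1.1 schedules the next rating after the last session. A patient who stops earlier and is not rated again has only the 10 to carry, which means no change. Replacement restores the number of completers but not the randomised comparison.

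**Working it through.** **1. The sections side by side, for a patient who stops before session 4**

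| Section | Rule |
|---|---|
| 8.1 | analysed, last observation carried forward |
| 6.4 | excluded from study and analysis |
| 9.3 | not in the analysis population |
| 9.4.2 | no rule |
| 9.4.3 | excluded (secondary endpoints) |
| 7.1 | stays in the study, remaining procedures completed |
| 1.1, 6.1.2 | withdrawn if side effects become limiting, or if patient or investigator decides to stop rTMS |
| 7.2 | replaced if treated and later withdrawn |

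**2. The plan's own figure.** Inputs from 9.2: effect 0.9 SD, 80% power, 5% level (two-sided assumed). Normal approximation: 2 × (1.960 + 0.842)² / 0.9² = 19.4, so 20 per arm and 40 in total, as stated. The t-test version gives 20.39, so 21 per arm; power at 20 per arm is 79.2%. Section 9.2 makes no allowance for exits.

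**3. Number analysed.** With replacement up to 40 completers and assumed exit q in both arms, exclusion analyses 40 patients. Carrying forward analyses 40/(1−q) = 44.4, 47.1 and 50 for q = 10, 15 and 20%.

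**4. Completers only, no true effect.** Assumptions: 20 completers per arm, loss q in one arm only, exit propensity correlated ρ with outcome, two-sided t-test at 5%. A t-test is used because the model in 9.4.2 takes "baseline HCS scores as covariate", and that covariate is 10 for everyone; age and sex are left out. The shift in the mean is ρ × φ(z)/(1−q), with z the upper-q normal quantile. At q = 10% and ρ = 0.5: 0.5 × 0.1755/0.90 = 0.10 SD. Type I error is from 200,000 simulated trials per case.

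| One-arm loss | Shift, ρ = 0.5 | Type I error |
|---|---|---|
| 5% | 0.05 SD | 5.3% |
| 10% | 0.10 SD | 6.1% |
| 15% | 0.14 SD | 7.1% |
| 20% | 0.17 SD | 8.5% |

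At ρ = 0 in both arms, or equal loss for the same reasons, it stays at about 5%.

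**5. Carrying forward the 10, no true effect.** Further assumptions: HCS mean 7–9, SD 3, one-arm loss 10–20%, no rating after stopping, leavers kept and also replaced; 100,000 trials per case.

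- ρ = 0.5: 5.0–6.0%.
- ρ = 0: 5.1–10.4%. The shift is roughly q × (10 − mean)/SD. At mean 7 this is q × 3/3 = 0.10, 0.15 and 0.20 SD against the arm with the loss. Simulation gives 0.10, 0.14 and 0.19 SD, with type I error 6.3, 8.0 and 10.4%. Completers are unbiased here.

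**6. Direction.** Assume a true difference of 0.9 SD, sham improvement of 0.4 SD (so active 1.3 SD), and 10% or 20% loss in the arm named.

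- Completers only, ρ = 0.7, worse outcomes leaving: 1.03 or 1.14 if they leave the active arm; 0.76 or 0.65 if they leave sham.
- Carrying forward, exit unrelated to outcome: active arm only, 0.9 × 1.3 − 0.4 = 0.77 or 0.8 × 1.3 − 0.4 = 0.64; sham only, 1.3 − 0.9 × 0.4 = 0.94 or 1.3 − 0.8 × 0.4 = 0.98.

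Each rule can err either way.

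**The case against.** The strongest reply is that this is an exploratory pilot (5.5, 9.2), that three sections exclude leavers and only one carries them forward, and that deleting the sentence in 8.1 would end the contradiction. It would, but it would leave a completer analysis with replacement, which is open to the bias in step 4.

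The drop-out definition in 8.1 sits under the responder criteria, so carrying forward might be meant only for the HCS <8 classification. That does not reconcile the sections, because 9.3 sets a single population for the analysis and removes the same patients.

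It is also fair that a mixed model does little by itself: for a leaver with no later rating it is in effect a completer analysis. Without an exit rating and without replacement, one-arm loss of 15 or 20% at ρ = 0.5 gives 6.9 or 7.9%. If 70% of leavers are rated, and that rating correlates 0.8 with the missing score and is entered as the final score (all assumed), it is about 5.1–5.5%. The gain comes from the rating, and this point stands.

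Three stronger readings are tempting but not supported:

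- A reader might infer that carrying forward always means no change. It does so only if no HCS follows stopping. Under 7.1 the remaining procedures continue, and the schema in 1.2 repeats the baseline questionnaires at the final visit.
- A reader might infer that patients who miss one or two sessions have no rule, because 8.1 lists as an exit "Patient misses more than two treatments in total". But 6.4 and 9.3 require all four sessions, and 7.2 makes inability to receive four a ground for withdrawal. Only the wording in 8.1 is loose.
- A reader might take complete dependence of exit on outcome in one arm as a worst case (9.5, 14.9 and 22.0% at 10, 15 and 20% loss). It is not a bound: equal loss for fully opposite reasons gives about 28, 56 and 83%. Nothing in the documents suggests either.

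**Conclusion.** The contradiction is explicit, concerns the primary endpoint, and is not resolved anywhere in the plan. Whether a leaver has a final HCS is also in conflict. That is enough to require a change before analysis.

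The case does not rest on a large bias. No exit rate is documented, and patients are inpatients enrolled for at most 4 days, so loss may be low and the bias is probably modest. Under the assumed one-arm losses and ρ = 0.5, neither rule exceeds a type I error of about 8.5%. Carrying forward does better than completers in that setting and worse when exit is unrelated to outcome. These are illustrations, not bounds; stronger or opposite-direction exit gives larger values.

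**What to change.** - Reconcile 1.1, 6.1.2, 6.4, 7.1, 7.2, 8.1, 9.3, 9.4.1 and 9.4.3 into one rule. Whether stopping rTMS ends participation is for the sponsor to reconcile; no clinical rule on stopping treatment or on antipsychotics is proposed here.
- Make the primary set all randomised patients by assigned arm, keep replaced patients in it, and report exits by arm with reasons. Delete the exclusions in 6.4, 9.3 and 9.4.3 and the carry-forward sentence in 8.1.
- Add the HCS to the data collected at discontinuation in 7.1. Where possible without delaying care, collect and use HCS ratings after stopping, as 7.1 already allows.
- Analyse all available post-baseline HCS with a likelihood-based mixed model. State that it assumes data are missing at random and that a leaver with no later rating contributes nothing. State too that placing an exit rating at a post-treatment time point is an assumption, and test it by leaving that rating out.
- Report completers only as a sensitivity analysis. An analysis giving leavers unfavourable scores is optional.

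The cost is protocol and SAP wording plus one short rating per leaver. Some leavers will be too unwell to rate, and for them the missing-at-random assumption remains.

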6.5 CONCOMITANT THERAPY

N/A

6.5.1 RESCUE MEDICINE

N/A

7 STUDY INTERVENTION DISCONTINUATION AND PARTICIPANT DISCONTINUATION/WITHDRAWAL

7.1 DISCONTINUATION OF STUDY INTERVENTION

Discontinuation from rTMS does not mean discontinuation from the study, and remaining study procedures should be completed as indicated by the study protocol. If a clinically significant finding is identified (including, but not limited to changes from baseline indicated by a score of 3 (“mild”) or less for all four items of the positive symptom BPRS-subscale (Robinson et al., 2015)) after enrollment, the investigator or qualified designee will determine if any change in participant management is needed. Any new clinically relevant finding will be reported as an adverse event (AE).

The data to be collected at the time of study intervention discontinuation will include the following:

- Reason for discontinuation
- Positive symptoms BPRS-subscale rating
- BAVQ-R rating
- MRI measurements

The specimens of individuals for whom an extra vial of blood was extracted for potential serum antipsychotic concentration analysis that later do not consent to participate in the study will be destroyed immediately without being processed.

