- Male and female subjects 18 to 65 years of age
- DSM V diagnosis of schizophrenia (295.90), schizoaffective disorder (295.70) or brief psychotic disorder (298.80) confirmed by SCID-V interview currently experiencing AVH in the acute phases of the disorder as assessed with the revised Beliefs About Voices Questionnaire (BAVQ-R).
- Patient agrees to rTMS for AVH treatment for 1 day before standard medication therapy.
- Right-handedness assessed with the Edinburgh Handedness Inventory
- Patient is competent to provide informed consent
- Inpatient at the Zucker Hillside Hospital
- No history of seizures

Phase:

N/A

**Description of
Sites/Facilities Enrolling
Participants:**

Participants will be recruited through the Zucker Hillside Hospital in-patient clinic. Recruitment will only take place at this site and no sites outside of the United States are included.

**Description of Study
Intervention:**

All patients receive 1Hz of rTMS over the Sylvian parietal temporal area (area Spt) four times on 1 day (1 pulse/second and a total of 1'000 pulses: 16 minutes' protocol at 100% of motor threshold modified based on

Hoffman et al. (1999)). Area Spt will be localized via baseline structural imaging and our Localite TMS navigation system.

Subjects will be withdrawn from the study if side effects become limiting, or if either the patient or principal investigator determine that rTMS should be discontinued.

[figure not shown]
Study Duration: 18 months in total including 12 months for recruitment and measurements plus 6 months for data analysis.

Participant Duration: Each participant is enrolled for up to 4 days of measurements (minimum of 3 days).

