5 STUDY POPULATION

5.1 INCLUSION CRITERIA

In order to be eligible to participate in this study, an individual must meet all of the following criteria:

1. Provision of signed and dated informed consent form
2. Stated willingness to comply with all study procedures and availability for the duration of the study
3. Male or female, aged 18 to 65
4. Diagnosed with DSM V diagnosis of schizophrenia (295.90), schizoaffective disorder (295.70), or brief psychotic disorder (298.80), prone to AVH in the acute phases of the disorder

5. Willing to adhere to the rTMS regimen
6. Subtherapeutic antipsychotic serum level upon admission as per Nathan Kline Institute reference guidelines on antipsychotic therapeutic serum levels.
7. Agreement to adhere to Lifestyle Considerations (see section 5.3) throughout study duration

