8.3 ADVERSE EVENTS AND SERIOUS ADVERSE EVENTS

8.3.1 DEFINITION OF ADVERSE EVENTS (AE)

Adverse event means any untoward medical occurrence associated with the use of an intervention in humans, whether or not considered intervention-related (21 CFR 312.32 (a)).

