8.3.4 TIME PERIOD AND FREQUENCY FOR EVENT ASSESSMENT AND FOLLOW-UP

The occurrence of an adverse event (AE) or serious adverse event (SAE) may come to the attention of study personnel during study visits and interviews of a study participant presenting for medical care, or upon review by a study monitor.

All AEs including local and systemic reactions not meeting the criteria for SAEs will be captured on the appropriate case report form (CRF). Information to be collected includes event description, time of onset, clinician's assessment of severity, relationship to study product (assessed only by those with the training and authority to make a diagnosis), and time of resolution/stabilization of the event. All AEs occurring while on study must be documented appropriately regardless of relationship. All AEs will be followed to adequate resolution.

Any medical condition that is present at the time that the participant is screened will be considered as baseline and not reported as an AE. However, if the study participant's condition deteriorates at any time during the study, it will be recorded as an AE. Thus, in the case of a worsening of symptoms leading to a worsening of the patient's condition, antipsychotic medication can be given on the ward if the responsible MD thinks that this is necessary for the patient's health. Patients' well-being is the main priority even if this means the termination from the study because of the antipsychotic.

Changes in the severity of an AE will be documented to allow an assessment of the duration of the event at each level of severity to be performed. AEs characterized as intermittent require documentation of onset and duration of each episode.

The PI as well as the research coordinator assisting the PI will record all reportable events with start dates occurring any time after informed consent is obtained until 7 (for non-serious AEs) or 30 days (for SAEs) after the last day of study participation. At each study visit, the investigator will inquire about the occurrence of AE/SAEs since the last visit. Events will be followed for outcome information until resolution or stabilization.

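### The only numeric example of a clinically significant finding in section 7.1 most naturally describes improvement, and the adverse event sentence after it gives no direction

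*Combined protocol and SAP*

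**What the plan says.** Section 7.1 (Discontinuation of study intervention) describes what happens when a clinically significant finding is identified after enrolment. The list of such findings is expressly open-ended, but it holds only one example with a number: a change from baseline shown by a score of 3, labelled mild, "or less for all four items of the positive symptom BPRS-subscale". The stated consequence is that "the investigator or qualified designee will determine if any change in participant management is needed". The following sentence uses a slightly different term and reads: "Any new clinically relevant finding will be reported as an adverse event (AE)".

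Other sections bear on how this should be read:

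- **8.3.1** defines the AE: "Adverse event means any untoward medical occurrence associated with the use of an intervention in humans".
- **8.3.4** says that a medical condition present at screening "will be considered as baseline and not reported as an AE", but that if the participant's "condition deteriorates at any time during the study, it will be recorded as an AE".
- **9.1**, secondary hypothesis 2, treats a reduction on the BPRS positive-symptom subscale as the hoped-for effect of real rTMS.
- **1.1** (Synopsis) describes the population as "currently experiencing AVH in the acute phases of the disorder". **5.1** is looser: "prone to AVH in the acute phases of the disorder". Neither sets a minimum BPRS score for entry.
- **2.2.1, 7.2 and 8.3.4** deal with worsening of psychotic symptoms in words, without a BPRS threshold.

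**The concern.** A section on stopping the intervention would be expected to point staff at patients who are getting worse. The one number in 7.1 appears to do the opposite: in acutely ill inpatients, reaching mild or less on every positive-symptom item is a good result.

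Two things follow if that reading is right. First, the AE sentence comes directly after the example and states no direction, so a reader who treats the two as one rule would enter a responder's improvement as an AE. Such entries would feed the principal investigator's review of AE frequency and severity in 10.1.6. If real rTMS works as hypothesised, they would also tend to fall in the active arm. Second, these patients are off antipsychotics and worsening is a risk named in 2.2.1, yet the documents give no numeric BPRS threshold for worsening.

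**Working it through.** The plan states no figure to reproduce. The check concerns the direction of the threshold and how the AE sentence fits the AE rules elsewhere.

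**Step 1: direction of the scale.** Section 7.1 labels a score of 3 as mild, and 9.1 treats reduction as benefit. Lower is therefore better. I assume whole-point item scores; the documents do not give the item range.

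**Step 2: what the example requires.** It is a joint condition on four items, each at 3 or below:

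- maximum total that meets it = 4 × 3 = 12;
- one item at 4 or more is enough to fail it, whatever the change from baseline.

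**Step 3: which changes meet it.** The scores below are illustrative and do not come from the documents.

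| Baseline items | Later items | Total | Change | Direction | Meets the 7.1 example? |
|---|---|---|---|---|---|
| 5, 5, 5, 5 | 3, 3, 3, 3 | 20 to 12 | −8 | better | yes |
| 3, 3, 3, 3 | 6, 6, 6, 6 | 12 to 24 | +12 | worse | no |
| 2, 2, 2, 2 | 3, 3, 3, 3 | 8 to 12 | +4 | worse | yes |

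The third row marks the limit of the claim. A worsening patient can meet the example, but only if every item is still at 3 or below afterwards. With no BPRS minimum for entry and the looser wording in 5.1, such a patient cannot be ruled out. Improvement is thus the natural reading in a population hallucinating at entry, but not a logical necessity.

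**Step 4: the AE sentence against the AE rules.** Under 8.3.1 an AE must be untoward. Under 8.3.4 a condition present at screening becomes an AE only when it deteriorates. Section 7.1 refers to neither and adds no direction of its own. There are two ways to read it:

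- *The two sentences as one rule:* an improvement that meets the example is a finding, and the finding is reported as an AE. This conflicts with both 8.3.1 and 8.3.4.
- *The AE sentence governed by 8.3.1:* only untoward findings are reported, and nothing is misrecorded.

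**Step 5: could the example be a deliberate remission rule?** The documents give this little support. All four sessions fall on one day. The schema in 1.2 places the BPRS at baseline (Visit 2) and at the final assessment (Visit 4), after stimulation has ended. The withdrawal reasons in 7.2 include no improvement criterion.

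**Step 6: number of entries affected.** This cannot be derived. It depends on how staff read the two sentences and how many patients reach the threshold, and the documents give neither. N = 40 is not a safe ceiling either, because treated patients who leave are replaced (7.2) and 7.1 also collects a BPRS rating at discontinuation.

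**The case against.** The strongest reply is that the harm depends on a misreading. The two sentences use different terms. The BPRS example leads only to a discretionary decision on management, and only the second term leads to an AE report. To record improvement as an AE, a reader would have to equate the terms and overlook the definition in 8.3.1. Section 8.3.3.2 also has a clinician evaluate every AE. This stands, and it is why the count may be 0.

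Next, the example does not work as a gate. The list is open-ended, and worsening is covered by firmer provisions: participation ends under 2.2.1, 7.2 lists disease progression and suicidal or homicidal risk, and 8.3.4 records deterioration as an AE. That also stands; no worsening patient has been shown to be missed.

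The reach in practice is small too. On the schema, the example would usually be met once no stimulation is left to discontinue. An earlier rating is not excluded, since the table in 5.5 lists an unspecified clinical assessment on the treatment day.

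Finally, a finding can be clinically significant without being bad, so changing the example to worsening might reverse what the authors meant. The threshold carries a citation that was not available here. This part is weaker, for the reasons in step 5 of the working. Even if the authors did mean improvement, the AE sentence would still need a direction.

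**Conclusion.** The concern holds, as a minor point. The one numeric example in 7.1 most naturally identifies improvement, and the AE sentence beside it gives no direction. Read in sequence they contradict 8.3.1 and 8.3.4; read under 8.3.1 they do not.

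What can be shown is direction, not a count: a total of at most 12 across the four items meets the example, and any item at 4 or more does not. The conclusion assumes that higher item scores are worse, as 7.1 and 9.1 imply, and that patients mostly enter with active symptoms, as the synopsis says. Any effect would be on AE records and the safety review. The primary HCS analysis and the sample size are untouched. Confidence in the reading of the wording is high; whether any entry would be misrecorded is unknown.

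**What to change.** Amend two sentences in 7.1:

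1. Replace the example with worsening from baseline on the BPRS positive-symptom items. A numeric cut-off is optional and is for the study physicians to choose.
2. Limit the AE sentence to untoward findings or deterioration from baseline, with a reference to 8.3.1 and 8.3.4, so that a low BPRS score is treated as efficacy data.

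If the authors did intend the example to describe improvement, they should say so; the second change is needed in either case.

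The cost is a short amendment, which the Statement of Compliance requires the IRB to review and approve before use. Design, sample size and analysis do not change. Adding a numeric worsening cut-off would go further than wording, because it would create a new safety criterion.
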